UCL CTU supports the commitment that its trials adhere to the SPIRIT guidelines. As such, the protocol template is based on an adaptation of the Medical Research Council CTU protocol template (2012) and the Standard Protocol Items: Recommendations for Interventional Trials (SPIRIT) 2012 Statement for protocols of clinical trials. The SPIRIT Statement Explanation and Elaboration document version 6 can be referred to, or a member of UCL CTU Protocol Review Committee can be contacted for further detail about specific items.

1.1 Compliance

The trial will be conducted in compliance with the approved protocol, the Declaration of Helsinki (2008), the principles of Good Clinical Practice (GCP) as laid down by the Commission Directive 2005/28/EC with implementation in national legislation in the UK by Statutory Instrument 2004/1031 and subsequent amendments, the UK Data Protection Act, and the National Health Service (NHS) Research Governance Framework for Health and Social Care (RGF). Agreements that include detailed roles and responsibilities will be in place between the participating site and UCL CTU.

The Participating site will inform UCL CTU as soon as they are aware of a possible serious breach of the approved protocol or of the principles of GCP. For the purposes of this protocol a 'serious breach' is one that is likely to affect to a significant degree:

- The safety or physical or mental integrity of the subjects in the trial, or
- The scientific value of the trial.

1.2 Sponsor

UCL is the trial sponsor and has delegated responsibility for the overall management of the TREAT CASP study to UCL CTU. Queries relating to UCL sponsorship of this trial should be addressed to the Director, UCL CTU, or via the trial team.

1.3 Structured trial summary

Primary Registry and Trial Identifying Number	ISRCTN Registration Applied for
Date of Registration in Primary Registry	11-08-2013.
Secondary Identifying Numbers	Other identifiers besides the trial identifying number allocated by the primary registry, if any. These include: • NIHR Portfolio ID: 14991
Source of Monetary or Material Support	National Institute for Health Research Efficacy and Mechanisms Evaluation funding stream (Funder reference EME 10-90-22)
Primary Sponsor	University College London
Secondary Sponsor	Sponsor responsibilities for Trial Management are delegated to UCL CTU.
Contact for Public Queries	[contact]
Contact for Scientific Queries	[name]
	UCL Institute of Cardiovascular Science,
	[name],
	[name]
	[contact]
	Email: [contact]
	[name]
	UCL Institute of Cardiovascular Science,
	[name],
	[name] [contact]
	Email: [contact]
Public Title	Can Blood Pressure Measured Near the Heart Indicate Which Young People With Increased Blood Pressure Benefit Most From Blood Pressure Lowering Treatment?
Scientific Title	The Evaluation of blood pressure treatment stratified according to Central Aortic Systolic Pressure (CASP) in Young Hypertensive Patients - The TREAT CASP study - A Cardiovascular Screening Study Followed By A One Year Prospective Randomised Open Blinded Endpoint Clinical Trial and a one year observational follow-up study Comparing Standard Blood Pressure Lowering Therapy with Usual Care on Central Aortic Systolic Pressure and Left Ventricular Mass Index by Cardiac MRI in Young Men with Stage 1 Hypertension.
Countries of Recruitment	UK
Health Condition(s) or Problem(s) Studied	Stratification of young men with stage 1 hypertension for blood pressure lowering therapy
Intervention(s)	Active Treatment Arm
	Losartan 50mg tablets once daily up-titrated to 100mg once daily if necessary and/or with addition of amlodipine 5mg

	tablets once daily if required to achieve BP target.
	Comparator Usual Care: No treatment. This study does not use any placebo tablet.
	Study Duration: 12 Months
Key Inclusion and Exclusion Criteria	Men (18-54 years) with stage 1 hypertension (blood pressure 140-159/90-99mmHg), not currently treated for hypertension and with no concurrent cardiovascular disease or overt target organ damage.
Study Type	 Cross-sectional observational screening study followed by an interventional clinical trial & observational follow- up study. Clinical Trial design: Prospective Randomised Open Blinded Endpoint (PROBE) design Phase III/IV Randomisation: Computer generated simple randomisation with allocation of study number and indicate treatment or no treatment
Date of First Enrolment	Anticipated June/July 2013.
Target Sample Size	500 participants recruited into the screening study with 130 then going on to be randomised into the clinical trial and 65 entering the observational follow-up study
Primary Outcome(s)	Study primary outcome: Change in Left Ventricular Mass Index on cardiac Magnetic Resonance Imaging (cMRI) in the randomised clinical trial comparing active treatment with usual care. Metric/method of measurement – grams per metre squared Timepoint – Baseline and Study end (12 months following treatment initiation).
Key Secondary Outcomes	 Secondary outcomes: The following outcome measures will be assessed at baseline and study end (12 months following treatment initiation): 1. Change in Left Ventricular Mass to volume ratio on cMRI Metric/method of measurement – grams per millilitre cubed 2. Regional systolic & diastolic strain Metric/method of measurement – % change in dimension by cMRI myocardial tissue tagging 3. Interstitial Fibrosis using T1 mapping Metric/method of measurement – Fibrosis index by cMRI 4. Aortic distensibility on cMRI Metric/method of measurement (10⁻³/kPa) 5. Aortic & Carotid wall thickness on cMRI Metric (micometers)

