6.4.1 Arm A

6.4.1.1 Products

BP lowering therapy for the intervention group in the stage 2 randomised clinical trial will be prescribed according to current NICE guidance for people aged <55years. Treatment constitutes an angiotensin receptor blocker (losartan 50mg once daily) for all ethnic groups other than for younger black men of African or Caribbean descent for whom a calcium antagonist (amlodipine 5mg once

daily) is the recommended initial treatment. Both of these treatments are well tolerated, generic and established medications, widely used in routine clinical practice.

Treatment will be titrated according to the CASP value rather than brachial BP values and up-titrated to achieve a CASP value of <120mmHg and/or at least a 5mmHg reduction in CASP from baseline. Combination therapy (i.e. angiotensin receptor blocker plus calcium antagonist) is also permitted if required in order to achieve blood pressure target.

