If the study proceeds to the second stage, those stage 1 participants identified as constituting the HIGH CASP group will then be invited to participate in the randomised clinical trial (n=130, early 2015). At the same time, 65 participants from the LOW CASP group will be invited to participate in the observational follow-up study. Participants entering the randomised clinical trial will commence medication at randomisation, i.e. there is no need for a wash-out/run-in period as this is a trial in treatment naïve participants. Similarly, those entering the observational follow-up study will be entered immediately at their randomisation visit.

For people participating in either the stage 2 randomised clinical trial or the stage 2 observational follow-up study, the study measurements performed during the stage 1 screening study (except for documentation of medical/lifestyle history and physical examination, see section 6.3.1.7) will be repeated both at randomisation (baseline) and at study end (study close out, 12 months). Ambulatory blood pressure monitoring will also be performed at randomisation and study end for all participants in the stage 2 randomised clinical trial and the observational follow-up study. All ABPM measurements during the stage 2 randomised clinical trial and observational follow-up study however, will use a wrist-mounted device (BPro device, Healthstats, Singapore) rather than the arm cuff device (Spacelabs) used in the Stage 1 screening study. This is because the wrist-mounted BPro device allows simultaneous monitoring of both brachial and central blood pressure over the course of 24 hours (see section 6.10.1) and will be used to monitor the change in 24-hour ambulatory blood pressure over the RCT and the observational follow-up studies.

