6.7.1 Sample Size for the Stage 2 Randomized Clinical Trial

The Primary Outcome Measure for the Stage 2 randomised clinical trial is the change in left ventricular mass index from baseline to study end between the intervention group (BP lowering) and the no treatment (usual care) group. No published data is available relating to the effects of treatment upon LV mass in young men without established cardiovascular disease. Therefore the sample size for the RCT (study stage 2) is based on an analysis of previously published data investigating the effects of BP lowering treatment on MRI-determined LV mass index (LVMI) in people with existing cardiovascular disease. Analysis of data taken from 4 individual treatment studies comprising 7 active treatment arms in 627 individuals, mean age 60±3.4 years (51-54), indicates an average difference in LVMI between treatments (treatment versus no treatment) of 6.6g/m², SD 10.9g/m² [Appendix, table 2]. All treatments in the cited studies used inhibitors of the renin-angiotensin system and achieved moderate reductions in blood pressure (average reduction with treatment -8/-4.5 mmHg). Based on an anticipated difference in LVMI between treatments of 6.6g/m², SD 10.9g/m², power calculations indicate a sample size of 58 people per treatment arm will be required to show a difference with 90% power at p=0.05 in LVMI between the treatment and no treatment groups for the RCT (study stage 2). Recruitment of 65 individuals per treatment arm will allow for 10% drop-out between treatments.

6.7.1.1 Justification for the specified duration of the RCT in stage 2.

The duration of the stage 2 RCT in the TREAT CASP study is 12 months. Prior studies of LVMI change in response to BP-lowering therapy indicate that the majority of LVMI regression occurs within the first 12 months of treatment with very little additional change with longer follow-up (up to 5 years), ^(55,56). This is because LVMI regression is powerfully determined by the extent of the reduction in BP on treatment, and the BP change is maximal during the first year of therapy. Thus, the anticipated change in BP with treatment and the proposed study duration has been chosen to maximise the change in LVMI within a reasonable timescale for the RCT.

6.7.2 Sample size underpinning the STOP/GO check point at the end of the stage 1 Screening Study

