6.9 Assignment of Intervention

6.9.1 Allocation

6.9.1.1 Sequence generation

Assignment to treatment or no treatment (usual care) will be by random allocation, according to a computer generated random list (simple randomisation) using the web-based interface provided by the UCL CTU independent of the clinical research team.

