6.10.4 Statistical Methods

6.10.4.1 Statistical Analysis Plan:

Study data will be analysed at three time points:

- At the end of the stage 1 screening study, demographic, clinical chemistry and haemodynamic study data will be analysed in a cross-sectional analysis.
- After the initial cMRI, the STOP/GO checkpoint analysis will be performed and cMRI data will be analysed together with stage 1 study data in cross-sectional analyses.
- At the end of the stage 2 RCT and observational follow-up study primary, secondary and other endpoints will be analysed and a longitudinal data analysis will be performed.

6.10.4.2 Statistical Methods – Outcomes:

STAGE 1: Central aortic systolic pressure (CASP) distribution will be used to stratify participants as potential candidates for stage 2. Participants with CASP values above the 75th percentile will be candidates for randomisation into the trial. Simple, unrestricted randomisation will be used. Those with CASP less than the 25th percentile will be offered participation in the observational follow-up part of stage 2.

STAGE 2: All analyses for outcomes in the RCT will be carried out on the basis of the originally assigned groups, whether participants complete treatment or not as per CONSORT guidelines ⁽⁸⁷⁾. Multilevel mixed-effects linear regression models with a maximum likelihood estimator will be used and will account for the repeated measures nature of the data. These models are inherently robust to missing data, dealing with missing values in a similar manner to multiple imputation approaches.

The principal outcome for assessment will be change in LV mass index over the 1-year follow-up period. This will be compared between the two groups without adjustment and then with adjustment for potential confounders in multivariable models. Such additional variables will include, but not be limited to, age, brachial artery systolic pressure, smoking history and measures of adiposity such as BMI. Over-fitting of models will be avoided by careful attention to the adjusted r²

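### Simple randomisation leaves baseline LVMI balance to chance, and the first-listed analysis of change in LVMI neither adjusts for baseline LVMI nor names it as a covariate

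*Protocol*

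**What the plan says.** Three places in the protocol fix the allocation method. Section 1.3 has "Computer generated simple randomisation with allocation of study number and indicate treatment or no treatment". Section 6.9.1.1 describes a "computer generated random list (simple randomisation) using the web-based interface" of the trials unit. Section 6.10.4.2 removes any doubt: "Simple, unrestricted randomisation will be used". No blocking, stratification or minimisation is given. Where the protocol speaks of stratifying, it means selecting the HIGH and LOW CASP groups.

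Section 1.3 expects "130 then going on to be randomised into the clinical trial". Section 6.7.1 states that "a sample size of 58 people per treatment arm will be required to show a difference with 90% power at p=0.05", for a difference of 6.6 g/m² with SD 10.9 g/m², and adds: "Recruitment of 65 individuals per treatment arm will allow for 10% drop-out between treatments".

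On sequence, 6.3.1.8 and 6.6 place the cardiac MRI of the HIGH CASP group before the STOP/GO checkpoint. Only then, under 6.6, "those stage 1 participants identified as constituting the HIGH CASP group will then be invited to participate in the randomised clinical trial". The visit schedule puts the MRI visit ahead of randomisation.

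On analysis, 6.10.4.2 specifies mixed-effects models for the repeated measures. Change in LVMI over one year is compared between arms first unadjusted and then adjusted. The covariates named are age, brachial systolic pressure, smoking and adiposity. The list is left open, but baseline LVMI is not on it.

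**The concern.** Baseline LVMI is the baseline value of the primary endpoint, and it will be on file for every man before he is allocated. The plan uses it neither in the allocation nor, by name, in the analysis.

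Taking the change from baseline does not remove the effect of a baseline imbalance. Men with a high first reading tend to show a larger fall at the second, whatever their treatment. If the active arm starts higher by chance, an unadjusted comparison of change tends to flatter treatment; if it starts lower, treatment looks worse. At stake is the precision of the primary result, and how it can be read if the arms do differ visibly at baseline.

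**Working it through.** **Inputs**
- Target difference 6.6 g/m² and SD of change 10.9 g/m² (6.7.1).
- 130 randomised, 65 per arm, 58 evaluable per arm (1.3, 6.7.1).
- Cross-sectional SD of LVMI in young men, 11.8 g/m² (6.7.2).
- Study-average SDs in Appendix Table part A: 15.8 at baseline, 16.8 at study end, 10.9 for change.
- Two-sided 5% test (assumed).

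**1. The plan's own figure.** n per arm = 2 × [10.9 × (1.960 + 1.282) / 6.6]² = 57.3, so 58. With 10% loss, 58 / 0.9 = 64.4, so 65. Both stated figures reproduce. An exact t-test gives 89.9% power at 58 per arm.

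**2. Unequal arms.** With Binomial(130, 0.5), the 95% range for one arm is 54 to 76. After 10% loss, exact-t power is 90.1% at 65:65 and 89.3% at 54:76. Averaged over the binomial distribution it is 89.9%. Arm size is not a problem.

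**3. Chance imbalance in baseline LVMI.** SE of the baseline difference = SD × √(2/65).
- SD 11.8: SE = 2.07 g/m²; 95% range ±4.1 g/m²; P(gap > 3.3) = 11%.
- SD 15.8: SE = 2.77 g/m²; P(gap > 3.3) = 23%.

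**4. Effect of a gap on the unadjusted comparison.** Let B be baseline, F follow-up and D = F − B. Then Cov(B, F) = [Var(B) + Var(F) − Var(D)] / 2, and the slope of change on baseline is Cov(B, F) / Var(B) − 1. With equal variances at both visits this reduces to −Var(D) / [2 Var(B)]. The share of the variance of change explained by baseline is slope² × Var(B) / Var(D).

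| SDs used (baseline / end / change) | Slope | Shift for a 3.3 gap (g/m²) | Variance explained |
|---|---|---|---|
| 11.8 / 11.8 (assumed equal) / 10.9 | −118.81 / 278.48 = −0.43 | 1.4 | 21% |
| 15.8 / 15.8 (assumed equal) / 10.9 | −118.81 / 499.28 = −0.24 | 0.8 | 12% |
| 15.8 / 16.8 / 10.9 | 206.535 / 249.64 − 1 = −0.17 | 0.6 | 6% |

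Over repeated draws, the SD of the shift is |slope| × SE: 0.43 × 2.07 = 0.9 g/m² in the first row, 0.24 × 2.77 = 0.7 in the second and 0.17 × 2.77 = 0.5 in the third. The SE of the treatment difference itself is 10.9 × √(2/58) = 2.0 g/m².

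**5. Gain from adjusting for baseline LVMI.** Residual SD = 10.9 × √(1 − variance explained), which is 10.6 g/m² at 6% and 9.7 g/m² at 21%. At 58 per arm, exact-t power rises from about 90% to about 92% and 95% respectively.

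**6. Gain from stratifying allocation at the median of baseline LVMI.** For a normal variable, a median split removes a share 2/π of the variance of the baseline difference. The SE falls to 2.07 × √(1 − 2/π) = 1.25 g/m², and P(gap > 3.3) falls from 11% to about 0.8%.

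**The case against.** The best defence is that nothing here is invalid. Simple randomisation is unbiased, and the standard error and type I error of the unadjusted test already allow for chance imbalance. It also makes the next allocation impossible to predict. That has value in an open-label, single-centre trial where the study nurse performs the allocation and sees past assignments (6.9.1.3, 6.9.2). All of this stands, and it is why the allocation change is only optional.

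It can also be said that the covariate list is open, that 6.10.4.2 admits covariates of known biological importance, and that covariate choice is often settled in a statistical analysis plan. A mixed model with baseline LVMI as a response and equal baseline means imposed on the arms would be close to baseline adjustment. This stands in part. The protocol permits adjustment but does not commit to it, and it does fix the order, with the unadjusted comparison first.

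The upper shift of 1.4 g/m² combines a change SD from treated patients of mean age about 60 with a cross-sectional SD from young men. That is fair, so the full range of 0.6 to 1.4 g/m² should be read.

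Two stronger readings are tempting, and the documents support neither:
- A reader might note that an exact 65:65 split occurs in only 7% of draws and infer that the trial misses its sample size. The 65 per arm is a recruitment target; no section requires equal arms, and the average power cost is about 0.2 percentage points.
- A reader might infer that allocation has to balance the first-drug group, because losartan comes first for all groups "other than for younger black men of African or Caribbean descent for whom a calcium antagonist" is specified. The protocol does not give that group's share, and it does not say that descent predicts change in LVMI. The control arm is untreated, so it has no drug mix to match.

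**Conclusion.** The point holds as one of efficiency and interpretation, not as an error. Simple randomisation is acceptable here. The weakness lies in combining it with a first-listed comparison that ignores baseline LVMI, a measurement every randomised man already has. A gap of more than half the target effect arises in about one draw in nine at SD 11.8, and would move the unadjusted estimate by 0.6 to 1.4 g/m² against a standard error of about 2.0.

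These sizes assume that the protocol's SDs apply to this population, that LVMI is roughly normal and, for the 1.4 and 0.8 values, that variances are equal at both visits. Knowing every candidate in advance does not fix the final number, because men are invited and must consent again at randomisation, so some may decline. Those who are randomised nevertheless all come from the group already scanned.

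**What to change.** In 6.10.4.2, make the primary comparison that of 12-month LVMI (or change in LVMI) between arms, adjusted for baseline LVMI as a continuous covariate, and keep the unadjusted comparison as supportive. This costs one protocol sentence and no patients, visits or scans.

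Optionally, change 1.3, 6.9.1.1 and 6.10.4.2 together to 1:1 allocation in large blocks of randomly varying size, concealed in the trials unit's web system, stratified by baseline LVMI at the HIGH-group median, with the stratum in the model. This costs a different list and slight predictability late in a block, which matters somewhat more in an open-label single-centre trial. It would have to be settled before stage 2 opens. Baseline adjustment alone deals with most of the concern.

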1.4.7 Protocol Review Committee

Where: BP - blood pressure; CASP – Central Aortic Systolic Pressure; CKD – Chronic Kidney Disease; CVD – Cardiovascular Disease; LVMI – Left Ventricular Mass Index; MRI – Magnetic Resonance Imaging; TOD – Target Organ Damage,

3 Abbreviations

ABPM	Ambulatory Blood Pressure					
	Monitoring					
ACR	Albumin:Creatinine Ratio					
AE	Adverse Event					
ANOVA	Analysis of Variance					
AR	Adverse Reaction					
ARB	Angiotensin Receptor Blocker					
BMI	Body Mass Index					
BP	Blood Pressure					
BrBP	Brachial Blood Pressure					
BrSBP	Brachial Systolic Blood Pressure					
CASP	Central Aortic Systolic Pressure					
CI	Chief Investigator					
CKD	Chronic Kidney Disease					
cMRI	Cardiac Magnetic Resonance					
	Imaging					
CRF	Case Report Form					
СТА	Clinical Trial Authorisation					
CTIMP	Clinical Trial of an Investigational					
	Medicinal Product					
CTU	Clinical Trials Unit					
CVD	Cardiovascular Disease					
DMEC	Data Monitoring and Ethics					
	Committee					
DSUR	Development Safety Update Report					
ECG	Electrocardigram					
eCRF	Electronic Case Report Form					
eGFR	Estimated Glomerular Filtration					
	Rate					
EU	European Union					
FDA	(US) Food and Drug Administration					
FWA	Federal Wide Assurance					
GCP	Good Clinical Practice					
GP	General Practitioner					
IB	Investigator's Brochure					
ICH	International Conference on					
	Harmonisation					
IMP	Investigational Medicinal Product					
IRB	Institutional Review Board					
ITT	Intention to Treat					
LTFU	Lost to Follow-Up					
LV	Left Ventricular					
LVMI	Left Ventricular Mass Index					
MAR	Missing at Ramdom					
MESA	Multi-Ethnic study of					
	Atherosclerosis					
MHRA	Medicines and Healthcare products					

	Regulatory Agency
MoU	Memorandum of Understanding
MRI	Magnetic Resonance Imaging
NAE	Notifiable Adverse Events
NHS	National Health Service
NICE	National Institute for Health and
	Clinical Excellence
NIHR-	National Institute for Health
EME	Research – Efficacy & Mechanisms
	Evaluation funding stream
NPMA	N-Point Moving Average
PI	Principal Investigator
PIS	Participant Information Sheet
PROBE	Prospective Randomised Open
	label Blinded Endpoint
PWV	Pulse Wave Velocity
QA	Quality Assurance
QALY	Quality Adjusted Life Years
QC	Quality Control
QMP	Quality Management Plan
QoL	Quality of Life
R&D	Research and Development
RAPW	Radial Artery Pressure Wave
RCT	Randomised Controlled Clinical
	Trial
REC	Research Ethics Committee
SAE	Serious Adverse Event
SAP	Statistical Analysis Plan
SAR	Serious Adverse Reaction
SD	Standard Deviation
SMS	Short Message Service
SPC	Summary of Product Characteristics
SSA	Site Specific Assessment
SUSAR	Suspected Unexpected Serious
	Adverse Reaction
TIA	Transient Ischaemic Attack
TMF	Trial Master File
TMG	Trial Management Group
TMT	Trial Management Team
TOD	Target Organ Damage
ToR	Terms of Reference
TSC	Trial Steering Committee
UCL	University College London
UCLH	University College London Hospital
WHO	World Health Organisation
L	

4 **Glossary**

24-Hour Ambulatory Blood Pressure Monitoring – A technique for measuring blood pressure at regular intervals over a 24-hour period using a modified portable BP monitor.

Albumin:Creatinine Ratio - A clinical test of urine which gives an indication of kidney function

ANOVA - A statistical test comparing data from two or more different groups

ARB - Angiotensin Receptor Blocker - a type of blood pressure lowering medication

Body Mass Index - A standard index of body size

Calcium Blocker - a type of blood pressure lowering medication

Central Aortic Pressure - pressure in the ascending aorta

cMRI – cardiac magnetic resonance imaging – non-invasive imaging of the heart and large conduit arteries

ECG - Electrocardiogram, a standard clinical test evaluating the electrical activity of the heart

Estimated Glomerular Filtration Rate – A clinical blood test which gives an indication of kidney function

Left Ventricular Mass Index – A parameter measured by MRI indicating structure of the heart

Magnetic Resonance Imaging – A high-resolution non-invasive imaging technique

n-Point Moving Average – A mathematical technique for calculating Central Aortic Systolic Pressure from radial artery pressure waveforms

Prospective Randomised Open label Blinded Endpoint – a type of clinical trial design which allows a clinical trial to be performed in which both participants and study doctors/nurses involved in clinical care to know which treatments participants are taking.

Radial Artery Pressure Wave - A measurement of the pressure pulse at the wrist

Randomisation – A method which assigns people to study medication or no medication without introducing bias

Standard Deviation - A statistical measurement of data dispersion

Target Organ Damage – Evidence of structural/functional change to key organs or tissues

Titration – Adjustment of drug dose/addition of further drug to achieve BP target

5 Introduction

